1.0 Background

Aneurysmal subarachnoid hemorrhage affects 6-8/100,000 people every year⁴. In addition to the various medical comorbidities that accompany this disease, about 50% will experience angiographic narrowing of the cerebral arteries (radiographic vasospasm) and 20-30% will experience delayed ischemic neurologic deficit (DIND, formerly clinical vasospasm)¹. The onset of vasospasm is most commonly between days 4 and 14 after the hemorrhage. Patients afflicted with DIND may go on to suffer permanent neurologic deficits which can impair their quality of life or be fatal. Although there has been much advancement in the last 15-20 years in the ability to monitor and assess this condition, there has unfortunately been scarce progress in treating it effectively³.

The current mainstay of therapy is so-called hyperdynamic therapy, in which the patient's blood pressure is augmented and blood volume increased with the hope that resistance to flow can be overcome and the brain perfused². This comes with its own set of complications, such as cardiac injury and fluid overload. It is also important to note that this modality of therapy has never been validated in a randomized, controlled trial, though it is accepted as the standard of care in many institutions⁵. Patients that are refractory to medical therapy may undergo angiographic therapy with infusion of agents such as calcium-channel blockers or papaverine or in extreme cases, balloon angioplasty. Some groups, such as the Montreal Neurological Hospital, have used infusions of the drug milrinone (Hospira, Inc Lake Forest, IL) to counter cerebral vasospasm. The smooth muscle of cerebral blood vessels is rich in phosphodiesterase-III (PDE-III), making it a promising target for this drug⁶. Milrinone is currently FDA approved for the treatment of congestive heart failure as it has both vasodilatory and inotropic effects. It is thought that these same effects may be beneficial in cerebral vasospasm. Milrinone also has anti-inflammatory effects through inhibition of interleukins⁵.

Milrinone is known to be safe with a relatively low incidence of complications. The Montreal group had no patients (out of 88 presented) with complications from milrinone infusion for as long as 9 days. To date, no study has compared the current standard-of-care, hyperdynamic therapy, with milrinone in addition to standard treatment.

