2.0 Rationale and Specific Aims

The goal of this study is to assess the efficacy of milrinone as an agent to treat cerebral vasospasm by adding it to standard therapy. This will take the form of a randomized, controlled trial in which patients will receive either standard hyperdynamic therapy or hyperdynamic therapy + milrinone. The primary outcome of interest will be modified Rankin Scale (mRS) at 6 months (+/- 60 days). Secondary outcomes assessed will be need for angiographic therapy, mRS at 12 months (+/- 60 days), duration of vasospasm (in days), hospital and ICU lengths of stay, side effects/complications of both modalities of therapy, milrinone dose, name and dose of drug(s) used for intra-arterial injection, number of times angiographic therapy is required, vasopressor usage, and discharge disposition.

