Once the patient is randomized in the study, they will continue to undergo TCDs on a three times per week basis as per institutional protocol. This number, along with the patient's clinical status, will be followed until symptoms resolve. Angiographic therapy may be utilized as needed based on the patient's needs and judgment of the treating physician. If no symptoms are evidenced for 72 hours, then the milrinone/placebo infusion will be weaned at a rate of 0.25 mCg/kg/min every 24 hours until a rate of 0.25 mCg/kg/min is reached, then the infusion will be turned off after 24 hours at this rate. For patients receiving an initial dose of 0.25 mCg/kg/min and titrated up to 0.375 mCg/kg/min, the infusion will be weaned to 0.125 mCg/kg/min for 24 hours then turned off. The weaning will not occur at a rate faster than 0.75 mCg/kg/min over 72 hours. HHH therapy will be weaned according to the standard institutional protocol. If symptoms recur, the protocol will be restarted. Patients with severe, refractory symptoms may still undergo angiographic rescue therapy. Special dosing will be followed for patients with impaired renal function, based on creatinine clearance (CrCl), checked at some point during the current hospital admission and prior to study drug initiation. This will be as follows:

CrCl (mL/min)	Initial Dose	Titration Dose
Greater than 50 mL/min	0.75 mCg/kg/min	1.25 mCg/kg/min
41- 50 mL/min	0.5 mCg/kg/min	0.75 mCg/kg/min
31-40 mL/min	0.375 mCg/kg/min	0.5 mCg/kg/min
21-30 mL/min	0.25 mCg/kg/min	0.375 mCg/kg/min

Table 1 – Renal dosing parameters

This dosing schema is reflective of the Montreal protocol⁵. While the initial dose of 0.75 mcg/kg/min is less than the currently maximum approved dose of 1.13 mcg/kg/min for congestive heart failure, the maximum titration dose of 1.25 mcg/kg/min is above this. The Montreal group presented 88 patients who were given this same dosing titration with minimal side effects⁵, so the investigators believe this procedure to be safe.

Data will be collected and entered into the study database. See Appendix A for a list of data points that will be collected. mRS collection will be carried out at follow-up appointments in the office or over the phone depending on patient availability.

The infusion of the drug may pose risks, including hypotension, arrhythmias, tachycardia, chest pain, and headache. In a very small number of cases, patients may develop severe arrhythmias

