6.1.2 Serious Adverse Event (SAE)

A serious adverse event is any untoward medical occurrence resulting in one or more of the following:

- Results in death or ANY death occurring within 28 days of last dose of study drug (even if it is not felt to be drug related)
- Is life-threatening (defined as an event in which the patient was at risk of death at the time of the event; it does not refer to an event which hypothetically might have caused death if it were more severe)
- Requires inpatient hospitalization or prolongation of existing hospitalization

NOTE: Hospitalizations that are not considered SAEs are:

- Hospitalization planned prior to first administration of study drug

- Hospitalization for elective treatment of a pre-existing condition unrelated to the study medication
- Results in persistent or significant disability/incapacity
- Is a congenital anomaly or birth defect
- Is an important medical event (defined as a medical event(s) that may not be immediately life-threatening or result in death or hospitalization but, based upon appropriate medical and scientific judgment, may jeopardize the patient or may require intervention (e.g., medical, surgical) to prevent one of the other serious outcomes listed in the definition above). Examples of such events include, but are not limited to, intensive treatment in an emergency room or at home for allergic bronchospasm; blood dyscrasias or convulsions not resulting in hospitalization; or the development of drug dependency or drug abuse.

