8.0 Statistical Considerations

Sample size justification: Literature on the natural history and outcomes specifically of patients who suffer DIND is sparse. Based on our own experience, we expect to see mRS of 2 or less in approximately 50% of patients in the control group. With a sample size of 59 patients per group, the study will have 80% power to detect a 25% difference between the experimental and control groups (75% vs. 50% with mRS of 2 or less), assuming a two-sided chi-square test conducted at a 5% significance level.

The experimental and control groups will be compared for differences in baseline demographics and clinical characteristics using chi-square tests for categorical variables and Wilcoxon Rank Sum tests for ordinal and continuous variables. The primary outcome, mRS 2 or less at 6 months, will be compared between groups using chi-square tests. Secondary outcomes, including need for angiographic therapy, mRS 2 or less at 12 months, presence of side effects/complications, and discharge disposition will be compared between groups using chi-square tests, and mRS scores at 6 and 12 months, duration of vasospasm, and hospital and ICU lengths of stay will be compared between groups using Wilcoxon Rank Sum tests.

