Appendix A – Data Points for Milrinone Protocol

➤ **Demographics**

- Name
- DOB
- Age
- MRN
- Study ID#
- Gender
- Ethnicity
- Race

➤ **Past Medical History**

- HTN
- Smoker

➤ **Presentation/Pre-Intervention Data**

- Date of SAH symptom onset
- Date of hospital admission
- Time of hospital admission
- Hunt/Hess score on admission
- Fischer score on admission
- Location of aneurysm (side and vessel)
- Size of aneurysm
- # of aneurysms
- Modality of treatment indicated (clip/coil/both)
- Date of treatment procedure
- Time of treatment procedure

➤ **Post-Intervention Data**

- First date of elevated TCD
- Time of first elevated TCD
- Measurement of first elevated TCD
- Severity of spasm
- Mean TCD throughout hospitalization
- Max TCD throughout hospitalization
- Need for EVD
- Date of clinical diagnosis of vasospasm
- Time of clinical diagnosis of vasospasm
- Duration of spasm
- Date of end of spasm
- Evidence of ischemic changes on CT prior to study drug initiation (date/time)
- Evidence of ischemic changes on CT any time during hospitalization (date/time)
- Vasopressor usage
 - Drug(s) used
 - Duration of use

➤ **Study Drug Data**

- Date study drug initiated
- Time study drug initiated
- Duration of study drug exposure
- Study drug dose at initiation
- Was study drug titrated up?

- Hemodynamic parameters
- Creatinine clearance checked during current admission prior to study drug initiation
- Was study drug discontinued early due to complications?

➤ **Angiographic Therapy Data**

- Results of angiogram
- Severity of spasm on angiogram
- Intra-arterial drug use?
- Number of times angiographic therapy required

➤ **Complications**

- Hypotension
- Tachycardia
- Arrhythmias
- Chest pain
- Others at discretions of provider

➤ **Outcomes**

- Length of ICU stay
- Date of transfer to floor
- Date of discharge
- Length of hospital stay
- Discharge disposition
- Modified Rankin Score at 6 months
- Modified Rankin Score at 12 months
- Whether patient received milrinone or placebo

Figure 1

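### Section 8.0 gives no rule for deaths in its rank tests of hospital and ICU stay, so a stay ended by death counts as short and favourable; the handling of vasospasm duration after a death in spasm is not stated

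*Combined protocol and SAP*

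**What the plan says.** Section 2.0 of the combined protocol and SAP lists "duration of vasospasm (in days), hospital and ICU lengths of stay" among the secondary outcomes. Section 8.0 states the analysis: "duration of vasospasm, and hospital and ICU lengths of stay will be compared between groups using Wilcoxon Rank Sum tests". It sets no patients aside and gives a death no rank.

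No other section supplies a rule. Death appears in these places:
- Section 1.0 says the ischaemic deficit can leave permanent deficits "which can impair their quality of life or be fatal".
- Section 3.1 excludes patients who die before their aneurysm is treated, which is before randomisation.
- Section 6.1.1 has death as adverse event grade 5, and section 6.1.2 counts as serious an event that "Results in death or ANY death occurring within 28 days of last dose of study drug". Both concern safety reporting.

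Section 5.1 keeps in the final analysis patients whose infusion is stopped for low blood pressure or shock. It also says that Doppler measurements and clinical status "will be followed until symptoms resolve". Appendix A collects "Date of end of spasm", "Length of ICU stay", length of hospital stay, date of discharge and discharge disposition. It lists no date of death.

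**The concern.** Shorter is better on all three outcomes, but a hospital or ICU stay also ends when the patient dies. A rank test on the raw values cannot tell early recovery from early death. If one arm has more in-hospital deaths, and those who die have shorter stays than survivors, that arm gains on both stay outcomes. An arm that prevents deaths loses on them for the same reason. The stay results could then point the opposite way to mortality.

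Vasospasm duration has a different gap. A patient who dies in spasm never reaches resolution. The end date may be entered as the date of death, which gives a short value, or left blank, which drops the patient. The plan does not choose.

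**Working it through.** **The plan's own figure.** For 75% versus 50%, two-sided 5%, 80% power: n = [1.960·√(2·0.625·0.375) + 0.842·√(0.25 + 0.1875)]² / 0.25² = (1.342 + 0.557)² / 0.0625 = 57.7, so 58 per group. At the stated 59, power is 80.9%. The figure reproduces, and this point does not change it.

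**Inputs.** From section 8.0: 59 per arm, Wilcoxon rank sum test. Two-sided 5% is stated there for the primary test and is assumed here for the secondary tests. The documents give no mortality or stay figures, so the following are assumptions:
- in-hospital deaths m1 and m2 of 10% to 20% per arm;
- log-normal stays counted from admission, survivor median 18 days, log SD 0.5;
- theta, the chance that a patient who dies in hospital has a shorter stay than a survivor, from 0.60 to 0.90.

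**Why theta stops at 0.90.** In this model the median stay of those who die is 18·exp(−z·0.5·√2), where z is the normal quantile of theta. Theta 0.60, 0.65, 0.75 and 0.90 give 15.0, 13.7, 11.2 and 7.3 days; theta 0.999 gives 2.0 days. Section 1.0 puts vasospasm onset most commonly on days 4 to 14 after the haemorrhage. Section 4.0 randomises at clinical vasospasm, and section 3.1 excludes patients admitted already in spasm. Death at about 2 days does not fit that timeline. With onset assumed uniform on days 4 to 14 from admission, death 1 to 5 days later gives theta 0.78 to 0.90, and death 3 to 14 days later gives 0.54 to 0.67.

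**Wrong-direction result, identical survivor stays.** The chance that a patient in arm 1 has a shorter stay than one in arm 2 is P = 0.5 + (theta − 0.5)(m1 − m2). The null standard error of its estimate is √(119 / (12·59²)) = 0.0534. The chance of a significant result favouring arm 1 is about 1 − Φ(1.96 − (P − 0.5)/0.0534). With m1 = 20% and m2 = 10%:

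| Theta | P | (P − 0.5)/0.0534 | By formula | By simulation |
|---|---|---|---|---|
| 0.60 | 0.510 | 0.187 | 3.8% | 3.6% to 4.0% |
| 0.65 | 0.515 | 0.281 | 4.7% | 4.7% |
| 0.75 | 0.525 | 0.468 | 6.8% | 6.7% |
| 0.90 | 0.540 | 0.749 | 11.3% | 11% |

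The simulations used at least 20,000 trials per scenario, stays rounded up to whole days, and the tie-corrected test. The nominal value is 2.5%. With equal deaths, 10% in both arms, P = 0.5 and the rate is about 2.5% at every theta. With deaths ranked worst, the 20% versus 10% figure is 0.2%.

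**Masking of a real benefit.** Suppose a milrinone survivor has a 65% chance of a shorter stay than a control survivor, with deaths m1 = 10% on milrinone and m2 = 20% on control. Theta is measured against control survivors. Then P = 0.5·m1·m2 + m1(1 − m2)·theta + (1 − m1)m2·g + (1 − m1)(1 − m2)·0.65. Here g = Φ(0.385 − z) is the chance that a milrinone survivor has a shorter stay than a control patient who dies.

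| Theta | g | P | Power by formula | Power by simulation |
|---|---|---|---|---|
| 0.60 | 0.553 | 0.625 | 65% | 66% |
| 0.65 | 0.500 | 0.620 | 61% | 62% |
| 0.75 | 0.386 | 0.608 | 52% | 53% |
| 0.90 | 0.185 | 0.583 | 34% | 35% |

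Simulated power with no deaths is 82%. With deaths ranked worst, P = 0.01 + 0 + 0.18 + 0.468 = 0.658 and simulated power is 86%.

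**The case against.** **The harm is conditional and secondary.** This stands. With equal mortality and timing the false-positive rate is correct, and if those who die had longer stays than survivors the bias would reverse. Section 8.0 also compares discharge disposition and mRS scores by arm, so deaths need not be invisible beside the stay results. But no section links disposition or the safety record to the stay tests, and equal mortality cannot be presumed when comparing treatments of a condition that can be fatal.

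**Stronger readings that the documents do not support:**
- A reader might infer that all three tests, followed as written, rank an early death among the best outcomes. That follows for hospital and ICU stay. For vasospasm duration the end date may simply be blank.
- A reader might let theta approach 1.0, which raises the wrong-direction rate to about 15% and lowers power in the masking example to about 19%. That needs death about 2 days after admission, before the usual vasospasm window.
- A reader might conclude that the primary analysis is compromised. The plan says "The primary outcome, mRS 2 or less at 6 months, will be compared between groups using chi-square tests", and nothing directs that deaths be dropped. The test is sound if deaths count as failures. Stating that death by 6 months is mRS 6, and how missing mRS is handled, would be useful clarification but is not part of this point.
- A reader might take the section 3.1 exclusion on completing 6 months of follow-up as removing deaths. It is an eligibility criterion, reviewed before randomisation under sections 4.0 and 5.1.

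**Worst rank is only one choice.** This also stands. Days alive and out of hospital, or time to discharge alive with death as a competing event, would also close the gap. What is missing is a stated rule.

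**Conclusion.** The point holds for hospital and ICU stay. The stated test treats a stay cut short by death as favourable, and nothing elsewhere in the plan prevents this. For vasospasm duration the defect is an unstated rule.

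The direction of the bias needs only that those who die have shorter stays than survivors and that deaths differ by arm. Its size rests wholly on assumed mortality and stays. Across theta 0.60 to 0.90 it is modest at the lower end and material at the upper end, and the loss of power in the masking example is larger than the excess of wrong-direction results. The plan should be corrected before unblinding, because a rule chosen afterwards could alter the result. The sample size and the primary comparison are not in question.

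**What to change.** In section 8.0, state that hospital stay, ICU stay and vasospasm duration are compared in randomised patients as assigned, with these ranks:
- a patient who dies before hospital discharge, including on the floor after leaving the ICU, ranks worse than every survivor on both stay outcomes;
- a patient who dies before vasospasm ends ranks worst on duration.

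Tabulate in-hospital deaths and survivors' raw durations by arm beside these tests. Add date of death to the Outcomes list in Appendix A. Section 8.0 should also say how patients who withdraw and decline further data collection (section 7.0) enter these comparisons, since the ranking rule does not settle that.

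**Cost.** A few sentences and one data field, with no extra patients, visits or procedures. The worst-rank test mixes death with duration. At deaths of 20% versus 10% with identical survivor stays it rejects about 15% of the time against the arm with more deaths, so it must be read with the mortality table. It also loses some power when mortality is equal. With the same survivor benefit and 10% deaths in both arms, power is about 63%, against 68% to 73% for the raw test over theta 0.60 to 0.90.

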9.0 Privacy/Confidentiality Issues

All medical information about patients will be maintained in secure and encrypted electronic medical record systems. As mentioned above, each patient will be assigned a unique and arbitrary identifier. The index for the identifiers will be maintained on a secure device which is encrypted and kept behind a firewall at all times. All efforts will be made to prevent transmission of this information, however if it should need to be transmitted, encryption will be used. All efforts will be made to minimize dissemination of this information. All paper records will be kept stored in secure locations with locking enclosures.

Appendix A – Data Points for Milrinone Protocol

➤ **Demographics**

- Name
- DOB
- Age
- MRN
- Study ID#
- Gender
- Ethnicity
- Race

➤ **Past Medical History**

- HTN
- Smoker

➤ **Presentation/Pre-Intervention Data**

- Date of SAH symptom onset
- Date of hospital admission
- Time of hospital admission
- Hunt/Hess score on admission
- Fischer score on admission
- Location of aneurysm (side and vessel)
- Size of aneurysm
- # of aneurysms
- Modality of treatment indicated (clip/coil/both)
- Date of treatment procedure
- Time of treatment procedure

➤ **Post-Intervention Data**

- First date of elevated TCD
- Time of first elevated TCD
- Measurement of first elevated TCD
- Severity of spasm
- Mean TCD throughout hospitalization
- Max TCD throughout hospitalization
- Need for EVD
- Date of clinical diagnosis of vasospasm
- Time of clinical diagnosis of vasospasm
- Duration of spasm
- Date of end of spasm
- Evidence of ischemic changes on CT prior to study drug initiation (date/time)
- Evidence of ischemic changes on CT any time during hospitalization (date/time)
- Vasopressor usage
 - Drug(s) used
 - Duration of use

➤ **Study Drug Data**

- Date study drug initiated
- Time study drug initiated
- Duration of study drug exposure
- Study drug dose at initiation
- Was study drug titrated up?

- Hemodynamic parameters
- Creatinine clearance checked during current admission prior to study drug initiation
- Was study drug discontinued early due to complications?

➤ **Angiographic Therapy Data**

- Results of angiogram
- Severity of spasm on angiogram
- Intra-arterial drug use?
- Number of times angiographic therapy required

➤ **Complications**

- Hypotension
- Tachycardia
- Arrhythmias
- Chest pain
- Others at discretions of provider

➤ **Outcomes**

- Length of ICU stay
- Date of transfer to floor
- Date of discharge
- Length of hospital stay
- Discharge disposition
- Modified Rankin Score at 6 months
- Modified Rankin Score at 12 months
- Whether patient received milrinone or placebo

Figure 1

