3.1 Inclusion/Exclusion Criteria

Inclusion

- Subjects \geq 18 years of age
- Aneurysmal subarachnoid hemorrhage, proven on CT angiogram or digital subtraction angiography
- Aneurysm treated, either by endovascular embolization or surgical clip ligation
- Evidence of increased velocities on transcranial dopplers (TCDs) and/or radiographic evidence of vasospasm as seen on angiogram
- Cerebral vasospasm as demonstrated by patient's clinical exam (new focal deficit or change in mental status not attributable to any other cause)

Exclusion

- Recurrent subarachnoid hemorrhage
- Untreated ruptured aneurysm, for any reason
- Patients who die prior to treatment for aneurysm
- Patients who are not able to complete at least 6 months of follow-up
- Patients who are admitted already in vasospasm (i.e. a delayed admission)
- Creatinine clearance less than 20 ml/min
- Women with a positive pregnancy test or who are lactating
- Other comorbidity which may adversely affect patient outcome, at the discretion of the principal investigator

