4.0 Enrollment/Randomization

Location: IU Health Methodist Hospital, [name]

Process: Patients diagnosed with aneurysmal subarachnoid hemorrhage will be identified at the time of diagnosis and the research team will be contacted by the admitting team to monitor the patient. The patients will be consented and enrolled into the study as soon as possible following surgery or endovascular intervention, if the PI (or his assigned designee) determines the patient to meet all criteria other than evidence of vasospasm. A subject ID number, which is arbitrary, will be assigned to the patient once consented so that patient confidentiality may be protected. They will not, however, be randomized at this point. The patient's Legally Authorized Representative (LAR) will be contacted for consent if the patient is unable to provide it. If a LAR is not present at the bedside, initial contact may take place over the phone to establish a time to discuss the study and obtain consent in person. At the time of diagnosis of clinical vasospasm, the treating physician(s) will notify the research team. At this time, eligibility will again be reviewed with the PI (or his assigned designee) and the protocol orders will be signed and scanned to the pharmacy where they will be entered into CERNER and the pharmacy will randomize the patient to standard hyperdynamic therapy with placebo (normal saline) or standard therapy + milrinone. Randomization will take place at the time of protocol entry into CERNER. The diagnosis will be at the judgment of the treating physician and confirmed by the PI (or his assigned designee). Providers and patients will remain blinded to the drug. An index of which patients received the drug will be maintained by pharmacy services.

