5.1 Study Procedures (see Figure 1)

Every effort will be made to initiate the protocol as soon as possible following confirmation of diagnosis and all eligibility criteria and to deliver the drug or placebo to the patient within two hours of order placement/protocol initiation. Diagnosis of clinical vasospasm will be at the

discretion of the treating physician or practitioner, and verified by the PI (or his assigned designee). The pharmacy services will then randomize the patient to receive either milrinone or placebo (normal saline). All patients will undergo treatment per the institutional protocol, which is to infuse fluids (crystalloid or colloid) at an increased rate to maintain a central venous pressure greater than 8 mmHg and progressive increase in blood pressure either by removing antihypertensive medications or using vasopressors, with the addition of milrinone or placebo based on randomization. Standard protocol in our institution calls for progressive increase of systolic pressure until symptoms subside, up to 220 mmHg. All patients will receive an infusion of milrinone or placebo at 0.75 mCg/kg/min. If no improvement is noted within 24 hours, the infusion will be increased to 1.25 mCg/kg/min. All patients in both groups will receive the same infusion at the same rate with the same parameters for increase of dose and for weaning (see below). The drug will be ordered by the physician and provided by pharmacy services in the standard institutional preparation. These parameters are the same as those used at the Montreal Neurological Hospital.

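### Neurological severity at randomisation is not a listed data point: the only clinical grade, Hunt/Hess, is taken at admission and always predates the deficit that qualifies the patient.

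*Combined protocol and SAP*

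**What the plan says.** Section 3.1 requires vasospasm shown by the clinical examination: "new focal deficit or change in mental status not attributable to any other cause". It excludes patients who arrive already in vasospasm. Section 1.0 gives the usual timing: "The onset of vasospasm is most commonly between days 4 and 14 after the hemorrhage".

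Section 4.0 ties randomisation to that event. Consent comes earlier, but "At the time of diagnosis of clinical vasospasm, the treating physician(s) will notify the research team"; eligibility is then reviewed again, and "Randomization will take place at the time of protocol entry into CERNER". The PI or a designee confirms the diagnosis.

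Section 5.1 makes the titration step depend on the clinical course: "If no improvement is noted within 24 hours, the infusion will be increased". It also says that clinical status is followed until symptoms resolve, without naming a scale. For the data set it says: "See Appendix A for a list of data points that will be collected".

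In Appendix A the one clinical grade is "Hunt/Hess score on admission". The Fisher score, also at admission, is radiographic. Section 8.0 plans tests of baseline demographics and clinical characteristics between groups, and an unadjusted chi-square test of mRS 2 or less at 6 months.

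**The concern.** How impaired a patient is when study drug starts is plausibly a leading predictor of mRS 2 or less at 6 months. The plan requires that impairment for entry and relies on change in it at 24 hours, yet the list of data to be collected holds no measure of it at either point. The admission grade cannot stand in for it, because the deficit is by definition new since then.

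Three things are at stake:
- the precision that a strong baseline covariate offers in a trial of 118 patients;
- the ability to see, and correct for, a chance difference between arms in neurological severity;
- a record in the trial data of the deficit that made each patient eligible, and of the response that led to the titration decision.

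This is a separate matter from adjusting for admission grade. Admission grade is collected and could be added to a model at any time; a standardised score at randomisation has to be recorded when the patient is examined.

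**Working it through.** **1. What Appendix A holds, by time point**

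| Time point | Items listed | Measures neurological severity? |
|---|---|---|
| Admission | Hunt/Hess; Fisher | Hunt/Hess yes, but before the qualifying deficit |
| Before study drug | ischaemic changes on CT (date/time); creatinine clearance | No |
| Around diagnosis | date and time of clinical diagnosis; first elevated TCD (date, time, value) | No |
| No time stated | severity of spasm; severity of spasm on angiogram; haemodynamic parameters | Not stated: plain severity of spasm has no scale or date |
| 24 hours | whether drug was titrated up (yes/no) | No |

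No consciousness score, type of deficit or neurological scale appears at diagnosis, randomisation or 24 hours.

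**2. The plan's own figure**

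Inputs from section 8.0: 50% vs 75%, two-sided alpha 0.05, 80% power, 59 per group. Pooled rate = (0.50 + 0.75)/2 = 0.625.

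n per group = [1.960 × √(2 × 0.625 × 0.375) + 0.842 × √(0.25 + 0.1875)]² / 0.25² = 57.7, so 58. At 59 per group, power is 80.9%, by formula and by exact enumeration. The stated figure reproduces and does not depend on any baseline grade.

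**3. Chance imbalance**

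Assumption (not in the documents): half the patients have a severe deficit at randomisation.

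- SD of the between-arm difference = √(2 × 0.25/59) = 9.2 points.
- Exact binomial: P(difference of 15 points or more) = 11.7%; P(10 points or more) = 31%.
- At 30% prevalence these become 9% and 27%.

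**4. Effect of a 15-point imbalance on the observed difference**

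Further assumption: control-arm mRS 2 or less differs by 30, 40 or 50 points between mild and severe. A common odds ratio is set so that the overall rates are 50% and 75%.

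| Control-arm gap | Treated-arm gap | Average gap | Shift = 0.15 × average |
|---|---|---|---|
| 30 | 22.0 | 26.0 | 3.9 points |
| 40 | 28.7 | 34.4 | 5.2 points |
| 50 | 34.9 | 42.4 | 6.4 points |

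Using the control-arm gap alone would give 4.5 to 7.5 points. The average is the fairer figure because both arms contribute. Against the 25-point design difference, 3.9 to 6.4 points is 16% to 26%.

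**5. Power with and without adjustment**

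Simulation of 6,000 trials per setting, 59 per arm, same assumptions; Pearson chi-square against a likelihood-ratio test from a logistic model with severity.

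| Control-arm gap | Unadjusted | Adjusted |
|---|---|---|
| 30 | 80–81% | 83.9% |
| 40 | 80–81% | 86.7% |
| 50 | 80–81% | 89.4% |

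Repeat runs of 4,000 trials agreed to within about 1 to 2 points. The comparator is no adjustment at all, and the covariate is a clean mild/severe split, so these are upper figures.

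**The case against.** The strongest reply is that much is recorded close to randomisation, that the diagnosis is checked by a second person, and that randomisation needs no covariate to be valid. Most of this stands, and it rules out several stronger readings.

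- A reader might infer that nothing about the patient's state at randomisation is captured. Appendix A does not support that: the pre-drug CT item is a dated measure of brain injury, and TCD, timing and renal items are there too. Only neurological severity is missing.
- A reader might infer that the baseline comparison in section 8.0 describes patients only as they were at admission. Section 8.0 sets no such limit, and the pre-drug items can enter the table.
- A reader might infer that the information is lost for good, or that eligibility goes unchecked. The examination takes place, the PI or a designee confirms the diagnosis, and the medical record number is collected, so chart abstraction may be possible. The documents do not promise a standardised record, however, and unscaled notes are a weak substitute.
- A reader might infer that the primary test is biased. Randomisation prevents systematic imbalance, and the unadjusted chi-square keeps its error rate.

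Two further objections limit the size of the point. The power gain is measured against no adjustment, whereas age, Hunt/Hess, Fisher score and pre-drug CT are already collected and could supply part of it. And the Glasgow Coma Scale grades a focal deficit poorly, so a real score may fall short of the modelled split.

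None of this supplies a measure of the deficit itself. The listed items describe imaging, vessels, timing and kidneys, and plain severity of spasm is too undefined to rely on.

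**Conclusion.** The gap is real and limited. Because patients admitted in vasospasm are excluded, the only clinical grade precedes the qualifying deficit in every eligible patient, and no neurological severity at randomisation is listed. Nor is any examination finding listed behind the 24-hour decision.

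The sample size and the planned primary test are unaffected. On the stated assumptions, the loss is at most about 3 to 8 points of power relative to no adjustment. There is also about a 12% chance of an unseen imbalance of 15 points or more; one of 15 points moves the observed difference by about 4 to 6.5 points. The documents give no prognostic strength, so both figures are illustrative. The gain over covariates already collected is unknown and probably smaller. The change should be made because it is cheap and hard to replace later, not because the trial fails without it.

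**What to change.** In Appendix A, add two fields at the pre-randomisation eligibility review: the Glasgow Coma Scale (motor score if intubated) and the type of deficit (focal, mental status, or both). Take both from the examination already performed for eligibility. Record the same score when the 24-hour titration decision is made, and use it for description only, since it is measured after randomisation.

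In section 8.0, show the pre-randomisation values in the baseline table, and prespecify a logistic analysis of mRS 2 or less at 6 months adjusted for the pre-randomisation score.

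Cost: two or three fields on the data form and a sentence or two in section 8.0. No extra examination is needed, and no dose or clinical rule changes. Downsides: scores will be partial in some sedated or intubated patients, and the Glasgow Coma Scale captures a focal deficit only weakly, which is why the type of deficit is recorded beside it.
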